### 9.1. Efficacy Assessments

#### 9.1.1. Primary Efficacy Assessments

The primary efficacy measure is HbA1c change from baseline to Week 32.

#### 9.1.2. Secondary Efficacy Assessments

- HbA1c change from baseline to Week 12
- Fasting glucose change from baseline to Weeks 12 and 32
- Insulin dose change from baseline to week 12 and 32

#### 9.1.3. Appropriateness of Assessments

Efficacy and safety assessments included in this study are generally regarded as reliable and accurate with respect to the efficacy and safety assessments in individuals and populations with T2DM.

#### 9.1.4. Body Weight

Body weight will be measured at prespecified time points (see Schedule of Activities, Section 2). Study participants will be weighed in a light hospital gown or standard clinical research site scrubs at approximately the same time in the morning after an overnight fast and after evacuation of bowel and bladder contents, if possible. Weight will be measured once at screening (non-fasting) and recorded in the source document and eCRF. At lead-in and randomization (Visit 2 and Visit 3, respectively) and all subsequent visits indicated in the Schedule of Activities (Section 2), weight will be measured twice, with the study participant stepping off the scale between measurements. Both weight measurements will be recorded in the source document and the eCRF. Calibrated (within 6 months prior to study start) scales should be used. The same scale should be used for all weight measurements throughout the study and should not be moved during the conduct of the study.

## 9.2. Adverse Events

Investigators are responsible for monitoring the safety of study participants who have entered this study and for alerting Lilly or its designee to any event that seems unusual, even if the event may be considered an unanticipated benefit to the study participant.

The investigator is responsible for the appropriate medical care of study participants during the study.

Investigators must document their review of each laboratory safety report.

The investigator remains responsible for following, through an appropriate health care option, AEs that are serious or otherwise medically important, considered related to the IP or the study, or that caused the study participant to discontinue the IP before completing the study. The study participant should be followed until the event resolves, stabilizes with appropriate diagnostic evaluation, or is reasonably explained. The frequency of follow-up evaluations of the AE is left to the discretion of the investigator.

Lack of drug effect is not an AE in clinical studies, because the purpose of the clinical study is to establish treatment effect.

After the ICF is signed, study site personnel will record via eCRF the occurrence and nature of each study participant's preexisting conditions, including clinically significant signs and symptoms of the disease under treatment in the study. In addition, site personnel will record any change in the condition(s) and any new conditions as AEs. Investigators should record their assessment of the potential relatedness of each AE to protocol procedure, IP, via eCRF.

The investigator will interpret and document whether or not an AE has a reasonable possibility of being related to IP, study device, or a study procedure, taking into account the disease, concomitant treatment or pathologies.

A "reasonable possibility" means that there is a cause and effect relationship between the IP, study device and/or study procedure and the AE.

The investigator answers yes/no when making this assessment.

Planned surgeries and nonsurgical interventions should not be reported as AEs unless the underlying medical condition has worsened during the course of the study.

If a study participant's IP is discontinued as a result of an AE, study site personnel must report this to Lilly or its designee via eCRF, clarifying if possible, the circumstances leading to any dosage modifications, or discontinuations of treatment.

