Investigators are not obligated to actively seek AEs or SAEs in subjects once they have discontinued and/or completed the study (the study participant disposition CRF has been completed). However, if the investigator learns of any SAE, including a death, at any time after a subject has been discharged from the study, and he/she considers the event reasonably possibly related to the study treatment or study participation, the investigator must promptly notify Lilly.

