#### **9.2.1.1. Suspected Unexpected Serious Adverse Reactions**

Suspected unexpected serious adverse reactions (SUSARs) are serious events that are not listed in the IB and that the investigator identifies as related to IP or procedure. United States 21 CFR 312.32 and European Union Clinical Trial Directive 2001/20/EC and the associated detailed guidances or national regulatory requirements in participating countries require the reporting of SUSARs. Lilly has procedures that will be followed for the identification, recording and expedited reporting of SUSARs that are consistent with global regulations and the associated detailed guidances.

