#### **9.2.2.2. Allergic/Hypersensitivity Reactions**

All allergic or hypersensitivity reactions, including injection site reactions, will be reported by the investigator as either AEs or, if any serious criterion is met, as SAEs. Additional data, such as type of reaction and treatment received, will be collected on any AEs or SAEs that the investigator deems related to IP via an eCRF created for this purpose. IP should be temporarily interrupted in any individual suspected of having a severe or serious allergic reaction to IP (Section 8.1.2). IP may be restarted when/if it is safe to do so, in the opinion of the investigator. If IP is permanently discontinued, see Section 8.1.1 for procedures required in this situation.

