#### 10.3.4.1. Adverse Events

Adverse Events will be listed by study participant, actual term, preferred term, severity, and relationship to the treatment. AEs will be summarized as TEAEs (defined as events that are newly reported after randomization or reported to worsen in severity from baseline). The incidence of study participants with at least 1 TEAE and the incidence of TEAEs by preferred term and system organ class will be presented by treatment group. The frequency and

percentage of TEAEs will be presented. The incidence of study participants with at least 1 TEAE assessed as possibly related to the investigational drug will be summarized by treatment group, in addition to the incidence of these possibly related TEAEs by preferred term. In addition, a summary of TEAEs by severity will be presented descriptively by treatment group.

Reported and adjudicated CV AEs will be listed by study participant, and if there are a sufficient number of cases they may be summarized by treatment group.

All SAEs will be listed by study participant. If a sufficient number of SAEs are reported, incidence summaries similar to incidence of TEAEs will be included.

Discontinuations due to AE and TEAEs will be listed by study participant and summarized by treatment group.

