4.10.2. Adverse Events (AEs)

Adverse events will be summarized as treatment emergent AEs (TEAEs, defined as events that are newly reported after the first dose of study basal insulin or reported to worsen in severity from baseline) for the Safety Population and compared between treatments unless otherwise specified. The Medical Dictionary for Regulatory Activities (MedDRA) Lowest Level Term (LLT) will be used in determination of the treatment-emergent status. The maximum severity for each LLT during the baseline period will be used as baseline severity. All analysis will be performed on the data collected from the date of first dose of study drug to the end of the study (up to Visit 801).

The number and percentage of patients with TEAEs will be summarized by treatment using MedDRA PTs nested within System Organ Class (SOC). Events will be ordered by decreasing frequency within SOC.

The number and percentages of patients with TEAEs ($\geq 2\%$ before rounding) will be summarized by treatment using MedDRA PT (without regard to SOC). Events will be ordered by decreasing frequency.

A TEAE considered possibly related to study drug will be summarized, separately, by treatment group using MedDRA PT nested within SOC. Events will be ordered by decreasing frequency within SOC.

A by-patient listing of all AEs for the Safety Population will be created including, but not limited to, SOC, event PT, severity, and relationship to study drug for all randomized patients.

Discontinuations due to AEs will be summarized by PT and compared between treatment groups using Fisher's exact test for the Safety Population.

Summary of treatment emergent SAEs similar to summaries for the proportion of patients experiencing each reported TEAE by SOC will be included for the Safety Population.

All SAEs (including death) will be listed for the Safety Population.

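### Protocol section 9.2 defines a reasonable possibility of relatedness as an existing cause-and-effect relationship; read literally this is stricter than the term itself and may lead sites to under-attribute adverse events.

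*Protocol*

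**What the plan says.** Protocol section 9.2 tells the investigator to decide "whether or not an AE has a reasonable possibility of being related to IP, study device, or a study procedure". Other explanations, such as the underlying illness or another therapy, are to be weighed in that decision. The next sentence defines the key phrase: a reasonable possibility "means that there is a cause and effect relationship between the IP, study device and/or study procedure and the AE". The response is binary: "The investigator answers yes/no when making this assessment". Earlier in the same section, the item recorded in the eCRF is described as potential relatedness.

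Other sections use the investigator's view of relatedness in their own words:

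- Protocol 9.2.1 requires notification of a serious event that occurs after consent but before study product only if it is reasonably possibly related to a study procedure. For an event learned of after discharge, the condition is that "he/she considers the event reasonably possibly related to the study treatment or study participation".
- Protocol 9.2.1.1 describes SUSARs as "serious events that are not listed in the IB and that the investigator identifies as related to IP or procedure".
- Protocol 9.2.2.2 says that additional detail on allergic reactions "will be collected on any AEs or SAEs that the investigator deems related to IP".
- Protocol 10.3.4.1 plans the incidence of participants with at least one "TEAE assessed as possibly related to the investigational drug".
- SAP 4.10.2 states: "A TEAE considered possibly related to study drug will be summarized", separately by treatment group.
- SAP 4.10.3.4 summarizes and compares injection site reactions that the investigator judges related to study drug.

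**The concern.** The question sets a threshold of possibility; the definition states a fact. An event for which a causal link is plausible but not settled meets the question and fails the definition. With only yes and no available, there is no middle category to hold it.

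Two things are at stake. First, tables labelled as possibly related would not show what their label says if sites answered to the literal definition, and they would mix two standards if sites differed. Second, some information is collected or passed on only when the answer is yes. A later analysis cannot recover details of an allergic reaction that were never recorded.

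**Working it through.** No arithmetic on rates applies. The documents give no expected number of related events or SUSARs, and no rate of disagreement between the two readings. The check is a comparison of the texts.

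**Step 1: is the definition stricter than the term?** The question in section 9.2 asks about a reasonable possibility, and the eCRF item is called potential relatedness. The defining sentence says that a relationship exists, with no qualifier such as may, possible or suspected. Taken by itself it is stricter. It sets no standard of proof: neither proven nor established appears.

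**Step 2: which direction can the effect take?** Let P be the set of events that meet a possibility standard and C the set that meets the literal definition. Every event in C is also in P, so count(C) ≤ count(P), and the shortfall count(P) − count(C) is zero or positive. Sites that follow the possibility wording contribute a shortfall of zero. The documents give no upper bound.

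**Step 3: what depends on the answer, and is there another route?**

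| Use | Depends on relatedness | Route that does not depend on it |
|---|---|---|
| Related-TEAE summaries (protocol 10.3.4.1, SAP 4.10.2) | Yes | All TEAEs are also summarized, but this does not correct the related tables |
| Related injection site reactions (SAP 4.10.3.4) | Yes | All potential injection site reactions are also compared |
| Additional allergic-reaction data (protocol 9.2.2.2) | Yes | All reactions are reported as AEs, and SAP 4.10.3.5 searches all TEAEs; the additional detail has no other stated route |
| SAE before study product (protocol 9.2.1) | Notification only | All AEs after consent are recorded in the eCRF |
| SAE after discharge (protocol 9.2.1) | Yes | None stated |
| SUSAR definition (protocol 9.2.1.1) | As worded, yes | Any on-study SAE after study product goes to the sponsor within 24 hours (9.2.1); sponsor SUSAR procedures (9.2.1.1) and SAE review (9.4.9) apply |

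**Step 4: does the post-discharge condition matter?** Protocol 7.8.1 says that washout of LY3209590 may take up to 10 weeks. Section 5.1.1 places the safety follow-up visit about 6 weeks after the last dose. If the 10 weeks run from the last dose (an assumption), 10 − 6 = about 4 weeks of possible residual exposure fall after that visit. For a participant discharged then, the relatedness condition is the only stated trigger for notification.

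**Step 5: what is untouched?** The secondary safety endpoints in the protocol's objectives table are hypoglycemia, treatment-emergent serious adverse events and body weight. None uses relatedness. SAP 4.10.2 limits the adverse event analysis to the time from first dose to the end of study (up to Visit 801), so serious events before dosing or after discharge lie outside that count. HbA1c and the sample size do not involve relatedness.

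**The case against.** The best defence is that the sentence should be read with its neighbours. The investigator interprets, weighs alternative explanations and records potential relatedness; all of that is the language of possibility. The sentence may be meant only to say what kind of relation counts, namely a causal one and not mere timing. Appendix 1 draws that contrast when it defines an adverse event as temporally associated with product use, without need of a causal relationship. A site that reads it this way answers correctly, and nothing is lost.

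This reading is fair and may well be what was intended. It does not remove the inconsistency: the sentence is presented as the definition, and a careful site or monitor may apply it as written.

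The defence does rule out several stronger inferences:

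- A reader might infer that yes requires proven causation. The text sets no standard of proof.
- A reader might infer that related counts are too low. The documents show a risk and its direction, not a shortfall. Any percentage would rest wholly on assumed rates.
- A reader might infer that SUSARs will be missed. The SUSAR wording does turn on the investigator's call, but on-study serious events after dosing reach the sponsor regardless. The content of the sponsor's SUSAR procedures is not given.
- A reader might infer that under-attribution differs between arms, because the trial is open-label and one product is new. Nothing in the documents supports a size or direction for this.

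The phrases in sections 9.2.1 and 9.2.2.2 also differ from the defined term, so a site might not carry the strict definition over to them. This is a further reason to use one term.

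**Conclusion.** The point holds as an internal inconsistency in a working definition. Its consequence is possible under-attribution at sites that apply the sentence literally. The effect can only lower the related counts or leave them unchanged; its size cannot be derived.

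The exposed items are the related-TEAE tables, the related injection site comparison, the additional allergic-reaction data, notification of serious events before dosing and after discharge, and, to a limited extent, SUSAR identification. This conclusion assumes that at least some sites follow the definition as written and carry it into the sections that use related phrases. It is worth correcting because the remedy is simple and some of the information cannot be recovered later. It does not threaten the trial's efficacy conclusions or its secondary safety endpoints.

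**What to change.** Reword the defining sentence in protocol 9.2 so that a possible or suspected causal relationship is enough for yes. For example: *a reasonable possibility means that there may be a cause and effect relationship between the IP, study device and/or study procedure and the AE; causation need not be established.* Keep the yes/no response.

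Use that one relatedness term in protocol 9.2, 9.2.1, 9.2.1.1, 9.2.2.2 and 10.3.4.1 and in SAP 4.10.2 and 4.10.3.4. Align any eCRF completion guidance that repeats the definition.

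For events already assessed under the present wording, a footnote to the related-event tables stating the definition in force would let readers interpret the counts.

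The cost is one sentence, some harmonized terms, and somewhat more events classed as related and therefore reported or documented in detail. The design, the sample size and the planned models do not change.

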### 9.2.1. Serious Adverse Events

An SAE is any AE from this study that results in one of the following outcomes:

- death
- initial or prolonged in-study participant hospitalization

- a life-threatening experience (that is, immediate risk of dying)
- persistent or significant disability/incapacity
- congenital anomaly/birth defect
- important medical events that may not be immediately life-threatening or result in death or hospitalization but may jeopardize the study participant or may require intervention to prevent one of the other outcomes listed in the definition above. Examples of such medical events include allergic bronchospasm requiring intensive treatment in an emergency room or at home, blood dyscrasias or convulsions that do not result in in-study participant hospitalization, or the development of drug dependency or drug abuse.

All AEs occurring after signing the ICF are recorded in the eCRF and assessed for serious criteria. The SAE reporting to the sponsor begins after the study participant has signed the ICF and has received IP. However, if an SAE occurs after signing the ICF, but prior to receiving IP, the SAE should be reported to the sponsor as per SAE reporting requirements and timelines (see Section 9.2) if it is considered reasonably possibly related to study procedure.

Study site personnel must alert Lilly or its designee of any SAE within 24 hours of investigator awareness of the event via a sponsor-approved method. If alerts are issued via telephone, they are to be immediately followed with official notification on study-specific SAE forms. This 24-hour notification requirement refers to the initial SAE information and all follow-up SAE information. Study participants with a serious hepatic adverse event should have additional data collected using the eCRF.

Pregnancy (during maternal or paternal exposure to IP) does not meet the definition of an AE. However, to fulfill regulatory requirements, any pregnancy should be reported following the SAE process to collect data on the outcome for both mother and fetus.

Investigators are not obligated to actively seek AEs or SAEs in subjects once they have discontinued and/or completed the study (the study participant disposition CRF has been completed). However, if the investigator learns of any SAE, including a death, at any time after a subject has been discharged from the study, and he/she considers the event reasonably possibly related to the study treatment or study participation, the investigator must promptly notify Lilly.

#### **9.2.1.1. Suspected Unexpected Serious Adverse Reactions**

Suspected unexpected serious adverse reactions (SUSARs) are serious events that are not listed in the IB and that the investigator identifies as related to IP or procedure. United States 21 CFR 312.32 and European Union Clinical Trial Directive 2001/20/EC and the associated detailed guidances or national regulatory requirements in participating countries require the reporting of SUSARs. Lilly has procedures that will be followed for the identification, recording and expedited reporting of SUSARs that are consistent with global regulations and the associated detailed guidances.

## 9.2.2. Adverse Events of Special Interest

### 9.2.2.1. Hypoglycemia

Study participants will collect information on episodes of hypoglycemia starting from Visit 2 until the last study visit (Visit 801 or ET visit). For that purpose, study participants will be trained about signs and symptoms of hypoglycemia, how to treat hypoglycemia, and how to collect in study diary appropriate information for each episode of hypoglycemia according to the Schedule of Activities (Section 2). Site personnel will enter this information into the eCRF at visits indicated in the Schedule of Activities (Section 2).

Investigators should use the following definitions and criteria when diagnosing and categorizing an episode considered to be related to hypoglycemia (the PG values in this section refer to values determined by a laboratory or International Federation of Clinical Chemistry and Laboratory Medicine plasma-equivalent glucose meters and strips) (American Diabetes Association 2005):

- **Documented symptomatic hypoglycemia** is defined as any time a study participant feels that he/she is experiencing symptoms and/or signs associated with hypoglycemia, and has a PG level of  $\leq 70$  mg/dL ( $\leq 3.9$  mmol/L).
- **Asymptomatic hypoglycemia** is defined as any event not accompanied by typical symptoms of hypoglycemia but with a measured PG  $\leq 70$  mg/dL ( $\leq 3.9$  mmol/L).
- **Probable symptomatic hypoglycemia** is defined as an event during which symptoms of hypoglycemia are not accompanied by a PG determination (but that was presumably caused by a PG concentration  $\leq 70$  mg/dL [ $\leq 3.9$  mmol/L]).
- **Severe hypoglycemia** is defined as an episode requiring the assistance of another person to actively administer carbohydrate, glucagon, or other resuscitative actions. These episodes may be associated with sufficient neuroglycopenia to induce seizure or coma. Plasma glucose measurements may not be available during such an event, but neurological recovery attributable to the restoration of PG to normal is considered sufficient evidence that the event was induced by a low PG concentration.
- **Nocturnal hypoglycemia** is defined as any hypoglycemic event that occurs between bedtime and waking.
- **Total hypoglycemia** is defined as any event meeting the criteria for documented symptomatic hypoglycemia, asymptomatic hypoglycemia, or probable symptomatic hypoglycemia
- Cases of relative hypoglycemia are defined as symptomatic events during which the person reports any of the typical symptoms of hypoglycemia and interprets those as indicative of hypoglycemia, but a measured PG concentration  $> 70$  mg/dL ( $> 3.9$  mmol/L) is collected.

For additional analysis, hypoglycemia defined as glucose  $< 54$  mg/dL ( $< 3.0$  mmol/L) will also be considered.

If a hypoglycemic event meets the criteria of severe, it needs to be recorded as serious on the AE eCRF and reported to Lilly as an SAE.

In each case of suspected or confirmed hypoglycemia, it is important that the event be properly categorized, the effect of the intervention be assessed, and the frequency and duration of hypoglycemia be evaluated. The role of dietary changes and physical exercise (or any other contributing factor) in the development of an event should be established. The study participant should receive additional education, if deemed appropriate. Management of increased risk of hypoglycemia is described in Section 7.8.2.2.

